### **9.2.1 Study Sites**

The study will be based on existing data from the [REDACTED] database, which covers all insurance types and a large population size (9.4). Thus, selection bias can be minimized.

## **9.2.2 Study population**

The target population of the study are Japanese NVAF patients with concomitant CAD, who are prescribed with dabigatran, rivaroxaban, or warfarin. The source population of the study are Japanese patients in the Japan [REDACTED] database during the study period, which is from April 18th, 2011 to December 31st, 2020. The study population will be selected based on the following in/exclusion criteria:

### **Inclusion Criteria**

1.  $\geq 18$  years of age
2. Has one year of look-back period prior to the index date (defined as the first date of prescription for dabigatran, rivaroxaban, or warfarin during the study period)
3. New users of warfarin, dabigatran, and rivaroxaban, defined as patients without historic use of any oral anticoagulants during the look-back period
4. Has at least 1 diagnosis of NVAF during the look-back period prior to or on the index date
5. Has at least 1 diagnosis of CAD during the look-back period prior to or on the index date

### **Exclusion Criteria**

1. Diagnosed with end-stage renal disease, or undergo hemodialysis, or experience pregnancy during the study period
2. Initiate warfarin, dabigatran, rivaroxaban due to valvular AF, AF associated with mechanical valve malfunction or mechanical complication of heart valve prosthesis, or rheumatic AF
3. Underwent joint replacement procedures or diagnosed with venous thromboembolism during the look-back period prior to or on the index date
4. Prescribed with more than 1 OAC on the index date
5. Prescribed with more than 2 anti-platelet drugs per prescription (triple or quadruple anti-platelet use), or prescribed with any anti-platelet injection
6. Patients with missing or ambiguous age or sex information

## **9.2.3 Study visits**

This is a non-interventional study based on existing data, hence not applicable.

## **9.2.4 Study discontinuation**

This is a non-interventional study based on existing data, hence not applicable.

## **9.3 VARIABLES**

### **9.3.1 Exposures**

#### **Exposure:**

Respectively for Group 1, 2, and 3, the initiation of warfarin, dabigatran, or rivaroxaban during the study period (dosage and duration are not restricted).

The exposure is measured through drug prescription records, which is recorded as [REDACTED] Receipt Code. In the [REDACTED] database, information pertinent to exposure records include the date of dispensing, drug quantity, dose, number of days of prescription supply, and prescriber.

### **9.3.2 Outcomes**

Outcomes are recorded with the 10th Revision of the International Classification of Diseases (ICD-10) codes. In the [REDACTED] database, information related to outcomes include the date of occurrence, the number of events, and the severity. All outcomes are incident events after the index date.

#### **9.3.2.1 Primary outcomes**

[figure not shown]
##### **Primary outcome:**

- Fatal or non-fatal major bleeding (defined as any blood transfusion and/or any hospitalization with associated bleeding) in all three patient groups

#### **9.3.2.2 Secondary outcomes**

##### **Secondary outcome:**

- Composite outcome of stroke/SE/MI/all-cause mortality (inpatient) /major bleeding/major GI bleeding (hospitalization due to GI bleeding)/ICH in all three patient groups (the first occurrence of any of the component events counts as an event; this outcome indicates the net clinical benefit)

### **9.3.3 Covariates**

Covariates are recorded with the 10th Revision of the International Classification of Diseases (ICD-10) codes for disease diagnosis and [REDACTED] Receipt Code for medications.

#### **Covariates (collected at baseline):**

##### **Demographic characteristics**

- Age
- Gender (male/female/other)

##### **Ischemic and hematologic characteristics (if available)**

- CHA2DS2-VASc score
- HAS-BLED score

**Comorbidities (has at least 1 diagnosis before or on the index date during the look-back period)**

- Heart failure (yes/no)
- Peripheral arterial disorder (yes/no)
- Hypertension (yes/no)
- Diabetes (yes/no)
- Prior stroke/transient ischemic attack (TIA)/SE (yes/no)
- Cerebrovascular disease (yes/no)
- Myocardial infarction (yes/no)
- Acute Coronary Syndrome (yes/no)
- Unstable angina (yes/no)
- Bleeding history (yes/no)
- Renal dysfunction (yes/no)
- Hepatic dysfunction (yes/no)
- Cancers (yes/no)
- Peptic ulcer disease (yes/no)
- Obesity (yes/no)

**Baseline co-medication (had used the drug before or on the index date during the look-back period)**

- Anti-platelet drugs (include aspirin, clopidogrel, ticagrelor, prasugrel) (yes/no)
- The number of anti-platelet drugs per prescription (single antiplatelet, dual antiplatelet, none)
- Antiplatelet use duration (single antiplatelet use: 6 months to 1 year, single antiplatelet use: 1 month to 6 months, single antiplatelet use: <1 month, dual antiplatelet use: 6 months to 1 year, dual antiplatelet use: 1 month to 6 months, dual antiplatelet use: <1 month, none; measured from the first antiplatelet prescription to baseline)
- Nonsteroidal anti-inflammatory drugs (yes/no)
- Gastric secretion inhibitors (yes/no)
- Statins (yes/no)
- Heparins (yes/no)
- Proton pump inhibitor (yes/no)
- Antihypertensive drugs (yes/no)

**Baseline medical procedures (underwent the procedure before or on the index date during the look-back period)**

- Cardioversion procedures (yes/no)
- Ablation procedures (yes/no)
- Percutaneous Coronary Intervention or Coronary Artery Bypass Grafting (yes/no)

**9.4 DATA SOURCES**

The [REDACTED] database is one of the largest databases in Japan, collecting data from over 400 acute care hospitals which account for 25% of emergency hospitals in Japan. The database contains comprehensive medical record data,

blood test result data, insurance claims data, and pharmacy claims data, covering more than 35 million patients, 34% of whom are  $\geq$  65 years old. Each patient is assigned a specific identification number (ID) to which all inpatient and outpatient data are linked. The diagnosis is coded according to the 10th Revision of the International Classification of Diseases (ICD-10) codes or local disease codes.

The distribution of demographic characteristics, including age and sex, of patients registered in the [REDACTED] database is very similar to the distribution of these characteristics of patients visiting hospitals in Japan.

## **9.5 STUDY SIZE**

During the period from April 2011 to December 2020, there are roughly 17000, 11000, and 4000 NVAF adult patients with a medical history of CAD being respectively treated with either warfarin, rivaroxaban or dabigatran as the first OAC (defined as no history of OAC usage during the 12-month look-back period) within the [REDACTED] database.

According to a published paper based on the [REDACTED] database, the mean (standard deviation, SD) treatment duration of different drugs among new user groups ranged from 265 (263.8) to 868 (725) days, with the dabigatran group exposed to the treatment the longest [P20-03503]. According to the same article, the major bleeding rate for AF patients is 1.5 per 100 patient-years. In comparison, AF patients with concomitant CAD are more likely to fall under high or medium/high risk categories of the HAS-BLED score, a predictor of bleeding complications among AF patients, thus increasing the event rate for major bleeding about 2-3 times [P09-11669], [R11-4223]. Therefore, the major bleeding rate is assumed to be rather 3-4.5 per 100 patient-years among Japanese AF+CAD patients in the [REDACTED] database.

Furthermore, previous analysis concluded substantial superiority of dabigatran (HR=0.66, 95% CI 0.529-0.825) and rivaroxaban (HR=0.74, 95% CI 0.618-0.879) over warfarin in major bleeding among AF patients [P09-11669], [R11-4223]. The comparative rates of major bleeding between individual NOAC- and warfarin- treated patients should follow a similar trend among NVAF patients with concomitant CAD.

For dabigatran vs. warfarin, if the HR is assumed to be 0.66 and the average exposure time to be 1 year per patient, an event rate of 3 per 100 patient-years with 80% power will require a total sample size of 6050 patients and 3025 patients for each arm; an event rate of 4.5 per 100 patient-years will require a total sample size of 4040 patients and 2020 patients for each arm. To be conservative, the lower bound is selected and therefore each arm needs around 3025 patients.

Similarly, assuming the HR of rivaroxaban vs. warfarin is 0.74 and the average exposure time to be 1 year per patient, the lower-bound event rate of 3 per 100 patient-years with 80% power will require a total sample size of 9690 patients and 4845 patients for each arm.

Additionally, to balance the baseline characteristics between groups, truncated Inverse Probability of Treatment Weighting (IPTW) will be applied and therefore sample loss is expected. In NOAC vs. warfarin comparisons, if the sample loss due to IPTW truncation is assumed to be 20%, the sample sizes for dabigatran and rivaroxaban groups need to be greater than 3781 and 6056 respectively, which can be satisfied by the database.

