**c37044336-01**

Proprietary confidential information © 2021 Boehringer Ingelheim International GmbH or one or more of its affiliated companies

Name of company: Boehringer Ingelheim			
Name of finished medicinal product: Pradaxa, Xarelto			
Name of active ingredient: Dabigatran, warfarin, rivaroxaban			
Protocol date: Nov. 15th, 2021	Study number: 1160-0308	Version/Revision: 1.0	Version/Revision date: NA

major bleeding about 2-3 times [P09-11669], [R11-4223]. Therefore, the major bleeding rate is assumed to be rather 3-4.5 per 100 patient-years among Japanese AF+CAD patients in the [REDACTED] database. Furthermore, previous analysis concluded substantial superiority of dabigatran (HR=0.66, 95% CI 0.529-0.825) and rivaroxaban (HR=0.74, 95% CI 0.618-0.879) over warfarin in major bleeding among AF patients [P09-11669], [R11-4223]. The comparative rates of major bleeding between individual NOAC- and warfarin- treated patients should follow a similar trend among NVAF patients with concomitant CAD.
 
For dabigatran vs. warfarin, if the HR is assumed to be 0.66 and the average exposure time to be 1 year per patient, an event rate of 3 per 100 patient-years with 80% power will require a total sample size of 6050 patients and 3025 patients for each arm; an event rate of 4.5 per 100 patient-years will require a total sample size of 4040 patients and 2020 patients for each arm. To be conservative, the lower bound is selected and therefore each arm needs around 3025 patients.
 
Similarly, assuming the HR of rivaroxaban vs. warfarin is 0.74 and the average exposure time to be 1 year per patient, the lower-bound event rate of 3 per 100 patient-years with 80% power will require a total sample size of 9690 patients and 4845 patients for each arm.
 
Additionally, to balance the baseline characteristics between groups, truncated Inverse Probability of Treatment Weighting (IPTW) will be applied and therefore sample loss is expected. In NOAC vs. warfarin comparisons, if the sample loss due to IPTW truncation is assumed to be 20%, the sample sizes for dabigatran and rivaroxaban groups need to be greater than 3781 and 6056 respectively, which can be satisfied by the database.
			
Data analysis:	Descriptive analysis will be performed for describing patient demographic and clinical characteristics. Comparative analysis for		

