### **9.7.1 Main analysis**

Comparative analysis for primary and secondary outcomes will be conducted between treatment groups. The comparative analysis will follow a two-step approach. The first step will compare the baseline characteristics and clinical outcomes of individual NOAC (Dabigatran, Rivaroxaban) -versus warfarin-treated groups.

[figure not shown]
During the first step of the comparative analysis, the baseline characteristics of the individual NOAC groups will be balanced with the warfarin group to account for potential confounding effects. Propensity scores will be calculated based on multinomial logistic regressions, with all covariates being incorporated. Next, an inverse probability of treatment weighting (IPTW) method will be applied using the calculated propensity score to avoid sample size inflation and to ensure appropriate estimation of variances. Yet, the IPTW estimates can be heavily influenced by large weights, thus destabilizing the results. To increase the robustness of the model, weight truncation will be applied once the distribution of propensity score is available. The distribution of propensity scores will be described, based on which the cut-off points of weight estimates will be chosen. Lastly, the calculated stabilized IPTW (s-IPTW) estimates will be applied to obtain two comparative pairs of individual NOAC vs. warfarin groups, for which the baseline demographics, risk factors, and clinical characteristics will be compared

using the absolute standardized difference (ASD) pre- and post- IPTW to assess the balance and model robustness. A covariate (baseline demographics, risk factors, clinical characteristics) will be considered well balanced if the ASD is below 0.1.

A Cox proportional hazard regression model with the time since NOAC drug index date as the underlying timescale will be used to compute adjusted hazard ratios (aHRs) with 95% CIs. If substantial covariate imbalance between treatment group is noted assessed by a standardized difference  $>0.1$ , then outcome models will be further adjusted by covariates that are out of balance using multivariable Cox proportional hazards models.

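### The rivaroxaban sample size of 9690 does not follow from the stated hazard ratio of 0.74: it matches HR 0.72, and at 0.74 it gives about 73% power, not 80%

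*Protocol*

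**What the plan says.** Protocol 9.5 (Study size) takes the treatment effect from earlier results, which it reports as "rivaroxaban (HR=0.74, 95% CI 0.618-0.879) over warfarin in major bleeding among AF patients". It sets the event rate for the study population as a whole: "the major bleeding rate is assumed to be rather 3-4.5 per 100 patient-years among Japanese AF+CAD patients".

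The dabigatran comparison comes first. With HR 0.66, 80% power and one year of exposure, the protocol asks for 6050 patients in total at 3 events per 100 patient-years, and 4040 at 4.5.

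The rivaroxaban comparison is presented as the parallel calculation, "assuming the HR of rivaroxaban vs. warfarin is 0.74 and the average exposure time to be 1 year per patient". Its result is that "the lower-bound event rate of 3 per 100 patient-years with 80% power will require a total sample size of 9690 patients", with 4845 in each arm. After a 20% allowance for loss to weight truncation, the protocol concludes that "the sample sizes for dabigatran and rivaroxaban groups need to be greater than 3781 and 6056 respectively" and that the database can supply these numbers.

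The abstract repeats all of these figures. The SAP has no study size section; the footnote to its Table 3 shell refers back to Protocol 9.5.

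**The concern.** The two stated totals are out of proportion. The rivaroxaban calculation uses the same rate, exposure and power as the first dabigatran calculation; only the hazard ratio changes, from 0.66 to 0.74. The required number should then rise by a factor of about 1.90 under Schoenfeld's formula (ln(0.66)² / ln(0.74)² = 0.1726 / 0.0907). Under Freedman's it should rise by 1.88 ((1.74/0.26)² / (1.66/0.34)²). The stated totals rise by only 9690 / 6050 = 1.60.

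This is one of the two primary comparisons. If the total is too small, the 80% power claim is wrong as written. So is the figure of 6056, which is the criterion by which the protocol declares the database sufficient. Anyone who later checks the retained sample against that figure, after exclusions and common-support trimming, would accept a number that does not give the stated power.

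**Working it through.** **Inputs (Protocol 9.5 unless noted)**

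- Hazard ratios: 0.66 (dabigatran) and 0.74 (rivaroxaban), each against warfarin.
- Event rate: 3 per 100 patient-years (4.5 in the alternative dabigatran case), applied to AF+CAD patients overall.
- Exposure: 1 year per patient. Groups: 1:1. Power: 80%.
- Alpha: not stated. Two-sided 0.05 is assumed, in line with the plan in Protocol 9.7.1 that a Cox model "will be used to compute adjusted hazard ratios (aHRs) with 95% CIs".

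**Formula**

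Events = 4 × (1.960 + 0.8416)² / ln(HR)² = 31.40 / ln(HR)². Total patients = events / (rate × 1 year).

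**Step 1: reproduce the dabigatran figures**

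HR 0.66: 31.40 / 0.1726 = 181.8 events.

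- At 0.03: 6061 patients (stated 6050).
- At 0.045: 4041 patients (stated 4040).

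Both agree within 0.2%, which supports the formula, the two-sided 0.05 and the overall-rate reading.

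**Step 2: the same formula for rivaroxaban**

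HR 0.74: 31.40 / 0.0907 = 346.3 events, and 346.3 / 0.03 gives about 11,543 patients.

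| Quantity | Stated | Recomputed at HR 0.74 |
|---|---|---|
| Total | 9690 | 11,543 |
| Per arm | 4845 | 5,772 |
| Per arm / 0.8 | 6056 | 7,215 |

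If events are rounded up to 347, these become 11,567, 5,784 and 7,230. The recomputed total is 19% above the stated one (11,543 / 9690 = 1.19).

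**Step 3: power of the stated size**

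9690 × 0.03 = 290.7 events. Power = Φ(√(290.7 / 4) × 0.3011 − 1.960) = Φ(0.607) = 72.8%. Freedman's formula gives 72.2% and a two-proportion calculation gives 73.5%.

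**Step 4: what hazard ratio fits 9690**

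HR = exp(−√(31.40 / 290.7)) = 0.7199. Forwards, HR 0.72 needs 290.9 events, or 9698 patients. That is as close to 9690 as the dabigatran results are to theirs.

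**Step 5: other conventions at HR 0.74, rate 3 per 100**

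| Convention | Total patients |
|---|---|
| Freedman, overall rate | 11,718 |
| Two proportions, overall rate | 11,364 |
| 3 per 100 as the warfarin-arm rate | 13,116 to 13,649 |
| Schoenfeld, allocation 11:17 | 12,098 |
| One-sided 0.05, overall rate | 8,952 to 9,392 |
| One-sided 0.05, warfarin-arm rate | 10,332 to 10,838 |
| 3 per 100 as the rivaroxaban-arm rate | 9,614 to 9,990 |

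Only the last row comes close to 9690. Applied to dabigatran, that reading gives 4,770 to 5,026 against the stated 6050. No convention tested gives 6050, 4040 and 9690 together at the stated hazard ratios.

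**The case against.** The strongest defence of the figure is that 3 per 100 is the rate in the rivaroxaban arm. Warfarin would then have 3 / 0.74 = 4.05 per 100, Schoenfeld's formula gives 9818 patients, and 9690 has 79.5% power. But the same reading gives 4820 for dabigatran, 20% below the stated 6050, and section 9.5 sets the rate for AF+CAD patients generally. It repairs one figure by breaking another.

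The HR of 0.72 is an inference. A different rate or exposure could also have been entered: 9690 patients yield the 346.3 events needed at HR 0.74 if the rate were 3.57 per 100 patient-years, or exposure 1.19 years. The documents do not settle which input changed. What is established is that 9690 does not follow from the inputs stated.

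It can also be said that nothing practical depends on the number. The study takes all eligible patients from an existing database, about 11,000 on rivaroxaban and 17,000 on warfarin. With 20% loss in each group, 22,400 patients give 672 events and about 97% power at HR 0.74, ignoring the extra variance from weighting. For the 1:1 matched sensitivity analysis named in the abstract, the protocol sets no size threshold; 8,800 matched pairs would give about 93% power on the same simple assumptions. The dabigatran–rivaroxaban step will use a new calculation. These points stand and limit the consequence to the stated requirement. They do not make the requirement or its power claim correct.

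**Conclusion.** The concern holds. At HR 0.74 and the protocol's other inputs, the rivaroxaban comparison needs about 11,543 patients rather than 9690, and about 7,215 rivaroxaban patients rather than 6056 before the 20% loss. The stated size has about 73% power.

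This rests on two-sided alpha 0.05, 1:1 groups and the event rate applying to both arms together. None of these is spelled out as a formula in the protocol, but together they reproduce both dabigatran totals. That HR 0.72 was the value used is likely but not documented.

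The conclusion that the database is large enough survives, since 7,215 is still well below 11,000. The correction should be made because a stated sample size, its power and a derived adequacy threshold for a primary comparison are wrong as written. It does not put the comparison itself in doubt.

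**What to change.** In Protocol section 9.5 and in the abstract, do one of the following:

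- Keep HR 0.74 and replace 9690, 4845 and 6056 by about 11,545, 5,772 and 7,215 (or 11,567, 5,784 and 7,230 if events are rounded up to 347).
- If HR 0.72 or another rate or exposure was intended, state it and justify it against the 0.74 and the other inputs quoted in the same section.

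In either case, name the formula, state the two-sided alpha of 0.05 if that is what was used, and say that the event rate is the overall rate across both arms.

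The cost is corrected figures in two places and one added sentence. No extra patients and no change to design or analysis are needed. The stated requirement becomes less favourable but is still met.

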## **9.6 DATA MANAGEMENT**

The data management plan is summarized below. Full details of the data management plan are documented in a separate NIS-Data Management and Review Plan (NIS-DMRP).

The data will be managed by BI. Source code of data management and data analyses will be kept for inspection at least for five years after publication of the results.

## **9.7 DATA ANALYSIS**

For the purpose of this study, analyses will be conducted using [REDACTED]  
[REDACTED] from [REDACTED] and SAS statistical software (version 9.3 or higher).

Descriptive analysis will be performed for describing patient demographic and clinical characteristics. For categorical variables, the frequency (n) and percentage (%) of patients under each category will be calculated. For continuous variables, the mean, median, standard deviations, interquartile range and minimum and maximum will be summarized.

In comparative analysis, the number of patients, number of events, number of person-years, incidence rate, and incidence proportion will be reported for all outcomes. Incidence rate of each outcome for each treatment group will be reported as the number of events (counts the first event per patient) divided by the total number of person-years at risk during follow-up. In addition, the incidence proportion of each outcome for each treatment group will be reported as the number of events (counts the first event per patient) divided by the total number of patients at risk.

Incidence rate of each outcome for each treatment group will be reported as the main descriptive statistics.

Table shells are attached as Annex 3.

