The second step will determine whether the patient characteristics are comparable between dabigatran and rivaroxaban treatment groups and whether there is the required sample size for comparisons between dabigatran- and rivaroxaban-treated groups. If the database can fulfil the sample size requirement, analysis will move forward for comparative analysis between the two NOAC groups.

For each component outcome of all 3 groups, the event-free survival will be plotted with Kaplan-Meier curves after s-IPTW adjustments.

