**Table 3. Rates and Risks of Fatal/Non-fatal Major Bleeding**

	Comparison 1		Comparison 2		Comparison 3*	
	Dabig atran	Warfa rin	Rivaro xaban	Warfa rin	Dabig atran	Rivaroxab an
Rate						
Crude						
Number of patients						
Number of events						
Number of person-years						
Incidence Rate per 1,000 person-years (95% CI)						
Incidence Proportion (n (%))						
s-IPTW adjusted						
Number of patients						
Number of events						
Number of person-years						
Incidence Rate per 1,000 person-years (95% CI)						
Incidence Proportion (n (%))						

Proprietary confidential information © 2022 Boehringer Ingelheim International GmbH or one or more of its affiliated companies

PS-matched						
Number of patients						
Number of events						
Number of person-years						
Incidence Rate per 1,000 person-years (95% CI)						
Incidence Proportion (n (%))						
Hazard ratios						
s-IPTWAdjusted Hazard Ratio (95% CI, p value)						
PS Matched Hazard Ratio (95% CI, p value)						

\*Note: comparison 3 will be conducted if sample size is sufficient (see section 9.5 of protocol)

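### The incidence-proportion rows of Table 3 have no time horizon, so they are not comparable between drugs whose on-treatment follow-up differs in length (minor; the rates and hazard ratios are unaffected)

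*Protocol*

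**What the plan says.** - **Definition of risk.** Protocol 9.7 (Data analysis) says that "the incidence proportion of each outcome for each treatment group will be reported as the number of events", counting the first event per patient, "divided by the total number of patients at risk". No follow-up time enters the definition.
- **Main statistic.** The same section adds: "Incidence rate of each outcome for each treatment group will be reported as the main descriptive statistics".
- **Table 3.** The shell in SAP Annex 5 is titled "Rates and Risks of Fatal/Non-fatal Major Bleeding"; Protocol Annex 3 has the same shell. For each drug pair it gives patients, events, person-years, incidence rate with 95% CI and incidence proportion. This block appears three times: unadjusted, s-IPTW adjusted and PS-matched. Hazard ratios follow below.
- **Follow-up.** Protocol 9.2 and SAP 7.2.1 end follow-up at discontinuation (a 45-day refill gap), switching, loss to follow-up, the outcome, death or 31 December 2020. Entry is allowed from 18 April 2012 to that same last day.
- **Expected exposure.** Protocol 9.5 cites a published cohort from the same database in which mean (SD) treatment duration "ranged from 265 (263.8) to 868 (725) days, with the dabigatran group exposed to the treatment the longest".
- **Curves.** For each component outcome, Protocol 9.7.1 says "the event-free survival will be plotted with Kaplan-Meier curves after s-IPTW adjustments".
- **Death.** Protocol 9.2 makes death an end of follow-up except for the composite and for all-cause mortality as a component. SAP 7.2.1 and 11.1 list death without that exception.
- **Fixed horizon.** SAP 11.1 restricts follow-up to 3 years in one sensitivity analysis, which covers Cox models only.

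**The concern.** Events divided by patients estimates a risk only when everyone is followed for the same stated time. Here follow-up lasts as long as the patient stays on the index drug, and potential follow-up runs from days to more than 8 years depending on the entry date. If persistence differs by drug, the proportion mixes the bleeding rate with the length of exposure, and the drug that patients stay on longest collects the most events.

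Labelling two of the three blocks as adjusted or matched adds to the problem. The weights and the matching balance baseline covariates. They do nothing to the length of follow-up, yet the labels invite a direct comparison of the percentages. These rows are also the only absolute risks in the table, so they are what a reader would naturally carry into a benefit-risk statement.

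A smaller, separate matter concerns the component curves. Where death is treated as censoring, one minus Kaplan-Meier overstates the probability of having the event, because patients who have died are handled as if they could still bleed.

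**Working it through.** **Inputs.** From Protocol 9.5: bleeding rate r = 3 to 4.5 per 100 patient-years, HR 0.66 for dabigatran vs warfarin, mean durations of 265 and 868 days. In years of 365.25 days these are 0.726 and 2.376. Assumed: constant hazards. The death rate d is not in the documents and is varied from 1 to 10 per 100 patient-years.

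**Step 1, check of the rate and HR.** The plan states no absolute-risk figure to reproduce, so the inputs are checked against its sample size. Schoenfeld with 1:1 allocation, 80% power and two-sided alpha 0.05 (alpha is assumed; the plan does not state it):
- Events = (1.960 + 0.842)² / (0.25 × (ln 0.66)²) = 181.8.
- N = 181.8 / 0.03 = 6061 (stated 6050).
- N = 181.8 / 0.045 = 4041 (stated 4040).

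Both agree closely, so these inputs are being read as the plan uses them.

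**Step 2, same bleeding rate, different exposure.** The expected proportion is 1 − exp(−rT) for fixed exposure T, or r / (r + 1/T) for exponentially distributed exposure with mean T.

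| Rate per 100 patient-years | Exposure model | 265 days | 868 days | Ratio |
|---|---|---|---|---|
| 3 | fixed | 2.15% | 6.88% | 3.2 |
| 3 | exponential | 2.13% | 6.65% | 3.1 |
| 4.5 | fixed | 3.21% | 10.14% | 3.2 |
| 4.5 | exponential | 3.16% | 9.66% | 3.1 |

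The drugs are equally safe in every row; the whole difference comes from exposure.

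**Step 3, with the plan's treatment effect.** Comparator at 3 per 100, dabigatran at 0.66 × 3 = 1.98 per 100 for 868 days:
- Dabigatran: 1 − exp(−0.0198 × 2.376) = 4.60%.
- Comparator at 868 days: 6.88%, ratio 0.67, the right direction.
- Comparator at 265 days: 2.15%, ratio 2.1, the wrong direction.
- Break-even: the proportions are equal when 0.66 × 868 = comparator days, that is about 573 days. This does not depend on r and is the same under both exposure models.

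**Step 4, fixed horizon.** At 1 year, deaths ignored: 1 − exp(−0.0198) = 1.96% against 1 − exp(−0.03) = 2.96%, ratio 0.66. At 4.5 per 100: 2.93% against 4.40%, ratio 0.67. The agreement with the HR is restored whatever the mean exposure.

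**Step 5, death as a competing event.** Death censored: 1 − exp(−rt). Cumulative incidence: r/(r + d) × (1 − exp(−(r + d)t)). With r = 0.03:

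| Time | 1 − KM | Cumulative incidence, d = 0.01 | Cumulative incidence, d = 0.10 | Relative excess of 1 − KM |
|---|---|---|---|---|
| 1 year | 2.96% | 2.94% | 2.81% | 0.5% to 5% |
| 3 years | 8.61% | 8.48% | 7.45% | 1.5% to 16% |

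The relative excess is practically the same at r = 0.045.

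**The case against.** The strongest reply is that the plan already handles unequal exposure. Protocol 9.7 introduces the proportion as an addition and names the incidence rate as the main descriptive statistic. Table 3 shows person-years and the rate with its CI directly above each proportion, and the HR below. This stands, and it limits the point. A reader might infer that the primary comparison is biased, or that Table 3 as a whole would mislead. The documents do not support either: rates and Cox HRs account for time at risk, and only someone reading the proportion rows alone would be misled.

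A reader might also infer that follow-up in this study will differ threefold by drug. The documents do not say so. The 265 to 868 days are treatment durations in an earlier AF cohort, not follow-up in AF patients with CAD. Only the longest is tied to a drug, and the 265-day drug need not be a Table 3 comparator. Reversal needs a comparator below about 573 days, which nothing in the documents establishes. What remains is the mechanism, which requires only unequal exposure.

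It would likewise be too broad to say that all component curves censor death. Protocol 9.2 exempts all-cause mortality, and the composite as well. The curves are described as event-free survival, and the plan does not say that their complement will be reported as risk.

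Finally, Protocol 9.7.2 and SAP 11.2 are redacted and the complete table shells are in an attachment that is not visible, so fixed-time or competing-risk output there cannot be ruled out. That would not alter the definition in Protocol 9.7 or the visible Table 3 rows.

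**Conclusion.** The point holds as a minor fault confined to the absolute-risk rows. Followed exactly, the plan yields a risk without a time horizon that depends on how long patients stay on each drug, and presents it as adjusted and matched. The roughly threefold distortion is an upper illustration that pairs the extremes of a cited range under constant hazards; the true size depends on the exposure seen in this cohort.

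The competing-risk part is right in principle but secondary. It applies to major bleeding and the non-fatal components, rests on an assumed death rate, is slight at 1 year and grows with time. Because Protocol 9.9 says mortality is known only during hospitalisation, it can be corrected only in part.

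**What to change.** 1. In Table 3 and the matching tables for other outcomes, replace the incidence-proportion rows with cumulative incidence at 1, 2 and 3 years, with numbers at risk: s-IPTW weighted in the weighted block and estimated in the matched set in the matched block. If the crude proportion is kept for description, footnote it as having no time horizon and as not comparable between drugs.
2. For major bleeding and the non-fatal components, use the Aalen-Johansen estimator with inpatient death as the competing event, for both the table entries and the curves. Keep Kaplan-Meier for the composite and for all-cause mortality.
3. Align SAP 7.2.1 and 11.1 with the exception for death in Protocol 9.2.

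The cost is a table-shell edit and a few lines of SAS or R; no new data are needed. Two limits should be stated with the results. Deaths outside hospital stay unseen. Censoring at discontinuation or switching is still assumed to be uninformative given weights built from baseline covariates only, so a fixed horizon removes the unequal-length problem but not any drug-dependent reason for stopping.
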